6.7 Other Exploratory Analysis

6.7.1 Biomarker Analysis

Biomarker assessments will be evaluated as part of the study, which may include genomic and transcriptomic studies. Optional blood collections for DNA and mRNA sequencing will be performed and may be used for potential biomarker research. The biomarker analyses will not be covered in the plan and will be developed in a separate plan as needed.

6.7.2 COVID-19 Impact

A listing will be provided for the impact of COVID-19 on the execution of the study.

6.7.3 EQ-5D-5L and WPAI:ILI

Patient-reported outcomes associated with symptoms of ILI will be assessed at the specified time points. All participants will receive eDiary prompts to complete the EQ-5D-5L questionnaire on Day 1, Day 91, Day 181, Day 271, and Day 361 (Month 12)/EoS, and participants who report symptoms of ILI will receive eDiary prompts to complete EQ-5D-5L and WPAI: ILI questionnaires.

A separate analysis plan will be developed for analyzing these two endpoints (EQ-5D-5L and WPAI:ILI) of patient-reported outcomes.

6.8 Planned Analysis

The primary analysis of safety and immunogenicity will be performed after all participants have completed the Day 29 visit. All data relevant to the primary study analysis through the Day 29 Visit for immunogenicity and safety assessment will be cleaned and locked. visit .

A 6-month analysis may be performed once all participants complete the Day 181 Visit or the influenza season ends, whichever occurs later. All of safety, immunogenicity, and efficacy data will be cleaned and locked for the 6-month analysis.

Additional safety or efficacy analyses at other time points may be performed.

The above analyses will be performed by a separate team of unblinded programmers and statisticians. More details can be found in the study data blinding plan.

Final analysis of all safety, immunogenicity, and efficacy data will be performed once all participants complete the Day 361 (Month 12)/EoS Visit in descriptive nature.

Ongoing unblinded safety reviews by a DSMB will be conducted during the study on a periodic basis, as defined in a DSMB charter or as needed if potential safety concerns are identified.

7 Changes in the Planned Analysis

Not applicable.

8 References

Department of Health and Human Services (DHHS), Food and Drug Administration, Center for Biologics Evaluation and Research (US). Guidance for industry: Clinical data needed to support the licensure of pandemic influenza vaccines. May 2007a [cited 2021 Aug 19]. Available from: <https://www.fda.gov/media/73691/download>

Department of Health and Human Services (DHHS), Food and Drug Administration, Center for Biologics Evaluation and Research (US). Guidance for industry: Toxicity grading scale for healthy adult and adolescent volunteers enrolled in preventive vaccine clinical trials. September 2007b [cited 2021 Aug 19]. Available from: <https://www.fda.gov/downloads/BiologicsBloodVaccines/GuidanceComplianceRegulatoryInformation/Guidances/Vaccines/ucm091977.pdf>.

9 Appendices

9.1 Schedule of Study Procedures

Table 6: Schedule of Events

Visit Number		1	2	3	4	5	6	7	8	9	USV
Type of Visit/Contact	C	C	C	SC	SC	C	SC	SC/C	SC	SC/C	C
Month Timepoint						M1	M3	M6	M9	M12	Up to M12
Study Visit	Screening ¹	D1 (Baseline)	D4	D8	D15	D29	D91	D181	D271	D361/EoS	USV
Window Allowance (Days)	-28	N/A	-2	±3	±3	-7 to +3	±5	±14	±14	±14	N/A
Informed consent form, demographics, concomitant medications, medical history ²	X										
Inclusion/exclusion criteria	X	X									
Physical examination ³	X										
Vital signs ⁴	X	X									
Pregnancy testing ⁵	X	X									
Randomization		X									
Study vaccination (including 30-minute post-dosing observation period) ⁶		X									
Collection of Edmonton Frail Scale ⁷		X									
Blood collection for humoral immunogenicity		X ⁸				X		X ⁹		X ⁹	
Genomic sample (optional)		X ⁸									
Transcriptomic sample (optional)		X ⁸				X					

Visit Number		1	2	3	4	5	6	7	8	9	USV
Type of Visit/Contact	C	C	C	SC	SC	C	SC	SC/C	SC	SC/C	C
Month Timepoint						M1	M3	M6	M9	M12	Up to M12
Study Visit	Screening ¹	D1 (Baseline)	D4	D8	D15	D29	D91	D181	D271	D361/EoS	USV
Window Allowance (Days)	-28	N/A	-2	±3	±3	-7 to +3	±5	±14	±14	±14	N/A
Optional blood sample for potential biomarker analysis ¹⁰			X								
NP swab for virus detection ¹¹											X
eDiary activation for recording solicited ARs (7 days) ¹²		X									
Review of eDiary for solicited ARs				X							
Symptom Reporting eDiary activation ¹³		X									
Symptom Reporting eDiary for collection of symptoms of ILI ¹⁴		Once weekly									
Review of Symptom Reporting eDiary ¹⁵		Review participant recorded ILI starting on Day 1 through Day 361 (Month 12)/EoS									
Follow-up safety call				X	X		X	X ¹⁶	X	X ¹⁶	
eDiary collection of EQ-5D-5L ¹⁷		X	eDiary prompts ¹⁸								
eDiary collection of WPAI:ILI ¹⁹			eDiary prompts ²⁰								
Recording of unsolicited AEs		X		X	X	X					
Recording of SAEs, AESIs, and MAAEs, as well as AEs that led to discontinuation and relevant concomitant medications/procedures ²¹		X		X	X	X	X	X	X	X	X

Visit Number		1	2	3	4	5	6	7	8	9	USV
Type of Visit/Contact	C	C	C	SC	SC	C	SC	SC/C	SC	SC/C	C
Month Timepoint						M1	M3	M6	M9	M12	Up to M12
Study Visit	Screening ¹	D1 (Baseline)	D4	D8	D15	D29	D91	D181	D271	D361/EoS	USV
Window Allowance (Days)	-28	N/A	-2	±3	±3	-7 to +3	±5	±14	±14	±14	N/A
Recording of concomitant medications and non-study vaccinations ²²		X		X	X	X					
Recording of hospitalizations and outpatient treatment-related to or for the treatment of the MAAE or SAE ²³		X		X	X	X	X	X	X	X	X
Study completion										X	

Abbreviations: AE = adverse event; AESI = adverse event of special interest; AR = adverse reaction; C = clinic; COVID-19 = coronavirus disease 2019; D = day; eDiary = electronic diary; EFS = Edmonton Frail Scale; EoS = end of study; EQ-5D-5L = EuroQoL 5-dimension 5-levels; FDA = Food and Drug Administration; HRQoL = health-related quality of life; ILI = influenza-like illness; IM = intramuscular; M = month; MAAE = medically attended adverse event; N/A = not applicable; NP = nasopharyngeal; SAE = serious adverse event; SARS-CoV-2 = severe acute respiratory syndrome coronavirus 2; SC = safety call (or contact by electronic means); USV = unscheduled visit; WPAI:ILI = Work Productivity and Activity Impairment Questionnaire: Influenza-like Illness.

Note: In accordance with FDA Guidance on Conduct of Clinical Trials of Medical Products during the COVID-19 Public Health Emergency ([FDA 2020](#)), investigators may convert clinic visits to telemedicine visits with the approval of the Sponsor.

- The Screening Visit and Day 1 may be performed on the same day or a different day. Additionally, the Screening Visit may be performed over multiple visits if within the 28-day screening window.
- Verbal medical history is acceptable.
- Physical examination: A full physical examination, including height and weight, will be performed at the Screening Visit; symptom-directed physical examinations may be performed at other clinic visits. Interim physical examinations will be performed at the discretion of the investigator. Any clinically significant finding identified by a healthcare professional during clinic visits should be reported as an MAAE.
- Vital signs measurements: Systolic and diastolic blood pressures, heart rate, respiratory rate, and body temperature. The preferred route of temperature assessment is oral. On the day of vaccination, vital signs will be collected once before vaccination and once 30 minutes after vaccination. Vital signs may be collected at other clinic visits in conjunction with a symptom-directed physical examination.
- A pregnancy test either via blood or point-of-care urine test will be performed at the Screening Visit and before the vaccine dose on Day 1, if Day 1 is not on the same day as the Screening Visit. At the discretion of the investigator, a pregnancy test either via blood or point-of-care urine can be performed at any time. The participant's follicle stimulating- hormone level may be measured at the Screening Visit, as necessary, and at the discretion of the investigator, to confirm postmenopausal status.
- See [Table 2](#) for dose levels and vaccination groups. All participants will be randomized to receive a single IM injection.

7. Assessment of EFS will only be performed for participants aged 65 years and older. EFS is a brief, valid and reliable tool for the assessment of frailty across 9 domains: cognition, general health status, functional independence, social support, medication use, nutrition, mood, continence, and functional performance.
8. Samples for humoral immunogenicity and transcriptomics must be collected prior to receipt of vaccination on Day 1.
9. Samples for humoral immunogenicity on Day 181 and Day 361 (Month 12)/EoS will be collected for the first 1000 participants and analyzed in a subset. These participants will require a clinic visit on Day 181 and Day 361 (Month 12)/EoS, .
10. Biomarker plasma and biomarker serum samples will be stored for potential future biomarker assessment
11. The NP swab specimen(s) for pathogens, including influenza virus and other respiratory pathogens (e.g., SARS-CoV-2) will be collected any time from Day 1 to Day 361 (Month 12)/EoS if participants have protocol-defined- ILI or symptoms suggestive of COVID-19 or other upper or lower respiratory infection as defined in the ILI Case Definitions in [Section 3.2](#). If participants experience these signs or symptoms, they will be instructed to contact the clinic to have an NP swab collected for testing. Nasopharyngeal (NP) swabs may be collected as part of a home visit in lieu of a clinic visit. In the event that NP swabs during ILI cannot be collected, any available influenza and/or SARS CoV-2 testing results performed outside of the study should be captured in the eCRF.
12. The eDiary entries will be recorded at approximately 30 minutes after injection while at the clinic with instruction provided by the clinic staff. Study participants will continue to record in the eDiary for solicited ARs each day after they leave the clinic, preferably in the evening and at the same time each day, on the day of injection and the subsequent 6 days following injection. If the event starts during the solicited period, but continues beyond 7 days after dosing, the participant should notify the site to provide an end date and close out the event on the Reactogenicity page of the eCRF. If the participant reported an event after the solicited period (ie, after Day 7), it should be recorded as an AE on the AE page of the eCRF. All solicited ARs (local and systemic) will be considered causally related to dosing.
13. The Symptom Reporting eDiary will be activated for collection of ILI symptoms starting at Day 1 and lasting until Day 361 (Month 12)/EoS.
14. Symptom Reporting eDiary: Participants will be instructed to report via Symptom Reporting eDiary or by contacting the site if ILI symptoms have been experienced from Day 1 to Day 361 (Month 12)/EoS. If symptoms occur, the investigator must contact the participant to assess symptoms and ensure an NP swab is collected within 72 hours of symptom onset. If possible, NP swabs should be collected prior to initiation of antiviral therapy. If there is no response to an eDiary prompt for 2 consecutive entries, the clinic staff will attempt to contact the study participant by telephone.
15. Review of eDiary for recording of symptoms of ILI.
16. Participants in the subset require a clinic visit on Day 181 and Day 361 (Month 12)/EoS for sample collection.
17. EQ-5D-5L is a well-validated, reliable, standardized instrument for measuring non-disease-specific HRQoL. EQ-5D-5L consists of a short descriptive system questionnaire and a visual analogue scale (EQ-VAS). The short descriptive questions are designed to assess 5 dimensions of health including mobility, self-care, usual activities, pain/discomfort, and anxiety/depression. The EQ-VAS records the health status on a scale between 0 and 100, with 0 indicating the worst imaginable health and 100 indicating the best imaginable health.
18. All participants will receive eDiary prompts to complete the EQ-5D-5L at Day 1 (baseline), Day 91, Day 181, Day 271, and Day 361 (Month 12)/EoS. For participants reporting symptoms of ILI, the EQ-5D-5L responses will be collected using the eDiary on the day of the symptoms reporting (+1 day) and 5 days (+1 day) later.
19. WPAI consists of 6 questions, which can quantitatively assess the amount of absenteeism, presenteeism, overall work impairment, and activity impairment attributable to a patient's health issues based on a 1-week recall period. The WPAI is available in different versions, such as WPAI: Specific Health Problem (WPAI:SHP), which can be adapted to a specific disease.
20. For participants reporting symptoms of ILI, the WPAI over the previous 7 days will be collected using the eDiary 5 days (+1 day) following the start of ILI symptoms reporting.
21. Trained study personnel will call all participants to collect information relating to any MAAEs, AEs leading to study discontinuation, SAEs, AESIs, information on concomitant medications associated with those events, and any non-study vaccinations. All concomitant medications relevant to or for the treatment of an SAE, AESI, or MAAE will be recorded from Day 1 through Day 361 (Month 12)/EoS.
22. All concomitant medications and non-study vaccinations will be recorded through 28 days after IP injection (including receipt of any authorized or investigational COVID-19 vaccine).
23. All hospitalizations, outpatient/physician visits, emergency room/urgent care visits, and telemedicine visits associated with MAAEs or SAEs will be recorded from Day 1 through Day 361 (Month 12)/EoS.

9.2 Standards for Variable Display in TFLs

Continuous Variables: The precision for continuous variables will be based on the precision of the data itself. The mean and median will be presented to one decimal place more than the original results; the SD will be presented to two decimals place more than the original results; the min and max will be presented to the same precision as the original results. For model-based estimates, the results may be presented up to 3 decimal points, unless otherwise specified.

Categorical Variables: Percentages will be presented to 1 decimal place. If the count is 0, the percentage will not be displayed. If the count equals the denominator, the percentage will be displayed as 100.

9.3 Analysis Visit Windows for Immunogenicity Analysis

Immunogenicity Analysis will be summarized using the following analysis visit window for post-injection assessments:

Step 1: If the immunogenicity assessments are collected at a scheduled visit, the collected data will be mapped to the nominal scheduled visit, the data collected at scheduled visit will be used.

Step 2: If the immunogenicity assessments are not collected at the scheduled visits, assessments collected at an unscheduled visit will be used using the analysis visit windows described in [Table 7](#) below.

If a participant has multiple assessments within the same analysis visit, the following rule will be used:

If multiple assessments occur within a given analysis visit, the assessment closest to the target study day will be used.

If there are 2 or more assessments equal distance to the target study day, the last assessment will be used.

Table 7: Analysis Visit Windowing

Visit	Target Study Day	Visit Window in Study Day
Immunogenicity		
Day 1	1 (Date of Injection)	1, Pre-vaccination
Day 29	29	[2, 105]
Day 181	181	[106, 271]
Day 361	361	≥ 272

9.4 Imputation Rules for Missing Dates

Imputation rules for missing or partial start/stop dates of medication and non-study vaccinations are defined below:

1. Missing or partial medication start date:

If only Day is missing, use the first day of the month, unless:

The medication end date is on/after the date of first injection or is missing AND the start month and year of the medication coincide with the start month and year of the first injection. In this case, use the date of first injection.

If Day and Month are both missing, use the first day of the year, unless:

The medication end date is on/after the date of first injection or is missing AND the start year of the medication coincide with the start year of the first injection. In this case, use the date of first injection.

If Day, Month, and Year are all missing, the date will not be imputed, but the medication will be treated as though it began prior to the first injection for purposes of determining if status as prior or concomitant.

2. Missing or partial medication stop date:

- a. If only Day is missing, use the earliest date of (last day of the month, study completion, discontinuation from the study, or death).
- b. If Day and Month are both missing, use the earliest date of (last day of the year, study completion, discontinuation from the study, or death).
- c. If Day, Month, and Year are all missing, the date will not be imputed, but the medication will be flagged as a continuing medication.

Imputation rules for missing or partial start dates and stop dates of AEs are defined below:

Missing or partial start date:

If only Day is missing, use the first day of the month, unless:

- The AE end date is on/after the date of first injection or is missing AND the start month and year of the AE coincide with the start month and year of the first injection. In this case, use the date and time of first injection, even if AE time was collected.

If Day and Month are both missing, use the first day of the year, unless:

- The AE end date is on/after the date of first injection or is missing AND the start year of the AE coincides with the start year of the first injection. In this case, use the date and time of first injection, when time is available.

If Day, Month, and Year are all missing, the date will not be imputed. However, if the AE end date is prior to the date of first injection, then the AE will be considered a pre-treatment AE. Otherwise, the AE will be considered treatment emergent.

Missing or partial end dates will not be imputed.

9.5 Prior and concomitant categorization of a medication

Table 8: Categorization of Medication

Medication Start Date	Medication End Date	
	< Injection Date of IP	≥ Injection Date and ≤ Injection Day + 27 Days After Injection [1]
< Injection date of IP [2]	P	P, C
≥ Injection date and ≤ 28 days after injection	-	C
> 28 days after injection	-	-

C = Concomitant; P = Prior

[1] includes medications with completely missing end date

[2] includes medications with completely missing start date

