6.5.1 Recording of Concomitant Medications, Concomitant Vaccinations, and Concomitant Procedures

The following concomitant medication(s) and vaccine(s) must be recorded in the eCRF:

- Any vaccine (authorized or investigational) administered in the prior 12 months.
- All concomitant medications and non-study vaccines taken through 28 days after the IP injection. Antipyretics and analgesics taken prophylactically (ie, taken in the absence of any symptoms in anticipation of an injection reaction) will be recorded as such.

- Any authorized or investigational COVID-19 vaccine at any time before or during the study period after the IP injection.
- Any authorized influenza vaccine at any time during the study period after the IP injection.
- All concomitant procedures/surgeries at any time during the study period after the IP injection.
- Immunosuppressants or other immune-modifying drugs administered chronically (ie, more than 14 days in total) and systemic steroids (≥ 10 mg/day prednisone or equivalent) , administered at any time during the study period after the IP injection.
- Immunoglobulins and long-acting biological therapies that affect immune responses (eg, infliximab) and/or any blood products administered during the study period.
- Any concomitant medications relevant to or for the treatment of an SAE, AESI, or medically attended AE (MAAE) from Day 1 through Day 361 (Month 12)/EoS.
- The participant will be asked in the eDiary if they have taken any antipyretic or analgesic to treat or prevent fever or pain within 7 days after the IP injection, including the day of injection. Reported antipyretic or analgesic medications should be recorded in the source document by the clinic staff during the clinic visits after vaccination or via other participant interactions (eg, telephone calls).

Concomitant medications (including vaccinations) will be coded using the WHO Drug Global.

If a participant takes a prohibited drug therapy, the investigator and the CRO's medical monitor will make a joint decision about continuing or withholding the study vaccination of the participant based on the time the medication was administered, the drug's pharmacology and pharmacokinetics, and whether use of the medication will compromise the participant's safety or interpretation of the data. It is the investigator's responsibility to ensure that details regarding the concomitant medications are adequately recorded in the eCRF.

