6.2.4 Prior and Concomitant Medications and Vaccinations

Prior and concomitant medications and non-study vaccinations will be coded using the WHO drug dictionary (WHODD) version Mar 2022. Imputation rules for missing dates of medications and non-study vaccinations are detailed in [Section 9.4](#). The summary of concomitant medications will be based on the Safety Set.

Categorization of prior and concomitant medications are summarized in [Table 8](#) in [Section 9.5](#). An overall summary of medications and non-study vaccinations including the number and percentage of participants who take the following will be presented by vaccination group:

- Prophylactic antipyretics or analgesics medication up to 28 days post-injection
- Any concomitant medications and non-study vaccinations up to 28 days post-injection
- Non-study seasonal influenza vaccine up to 28 days post-injection
- Systemic steroids (≥ 10 mg/day prednisone or equivalent), immunosuppressants, immune-modifying drugs, immunoglobulins, and/or blood products administered at any time up to 28 days post-injection

The number and percentages of participants with at least one concomitant medication will be summarized by preferred terms and vaccination group. Prior, concomitant medications and non-study vaccination will be presented in a listing. Medications taken to prevent or treat pain or fever will also be presented in a listing. Concomitant procedures will be presented in a listing.

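### SAP Table 8 has no cell for a medication that overlaps Days 1–28 but has a known or imputed end date after Day 28, so read literally it drops out of the descriptive concomitant-medication summaries

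*SAP*

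**What the plan says.** SAP Section 6.2.4 refers to Table 8 (Section 9.5) for the categorization of prior and concomitant medications. Table 8 has two end-date columns. One is before injection; the other is headed "≥ Injection Date and ≤ Injection Day + 27 Days After Injection [1". The footnote to the second column reads "1] includes medications with completely missing end date". The three start-date rows are before injection, "≥ Injection date and ≤ 28 days after injection", and later than that. The legend has two classes, P (prior) and C (concomitant).

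SAP Section 9.4 sets the stop date used when one is incomplete. With only the day missing, the rule is to "use the earliest date of (last day of the month, study completion, discontinuation from the study, or death"). With day and month missing, the end of the year replaces the end of the month. With nothing recorded, "the date will not be imputed, but the medication will be flagged as a continuing medication".

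SAP Section 6.2.4 then plans, by vaccination group, a count of participants with any concomitant medication or non-study vaccination up to 28 days, and a preferred-term table of participants with at least one concomitant medication. It also has a separate line for systemic steroids, "immunosuppressants, immune-modifying drugs, immunoglobulins, and/or blood products administered at any time up to 28 days post-injection". SAP Section 6.1 defines the 28-day period as the day of vaccination plus 27 days. Protocol Section 6.5.1 requires chronic immunosuppressants and systemic steroids to be recorded if "administered at any time during the study period after the IP injection".

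**The concern.** A medication is normally concomitant if its interval overlaps the observation period. Table 8 instead requires it to end within that period or to have no end date at all. A drug taken on every day from Day 1 to Day 28 and stopped on Day 45 meets neither condition and receives no class.

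Two things follow. The classification depends on how complete the stop date is, and a better-documented record can be the one that is lost. It also depends on the date of the data lock, because a drug with no stop date at the Day 29 analysis may have one by the final analysis. Late end dates are foreseeable, since Protocol Section 6.5.1 keeps recording several drug classes after Day 28. At stake is whether the concomitant-medication tables give a correct and reproducible description of each arm.

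**Working it through.** The plan states no figure to reproduce. The check applies Table 8 literally to chosen start and end dates.

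**Inputs.** From SAP Section 6.1, study day = date − injection date + 1 on or after injection, so injection + 27 is study Day 28. From Table 8: three start rows, two end columns, and footnote 1 placing a completely missing end date in the second column. From SAP Section 9.4: the stop-date rules above.

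**Classification.**

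| Start | End | Result |
|---|---|---|
| Before injection | Day 28 (injection + 27) | P, C |
| Before injection | Day 29 (injection + 28) | no cell |
| Before injection | Day 46 (injection + 45) | no cell |
| Before injection | completely missing | P, C |
| Day 5 | Day 28 | C |
| Day 5 | Day 61 (injection + 60) | no cell |
| Day 5 | completely missing | C |

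One extra day of treatment, Day 29 instead of Day 28, takes a drug from concomitant to unclassified.

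**Effect of a partial stop date.** Take an illustrative injection on 20 June 2022. Injection + 27 days = 17 July 2022. Assume no earlier study exit or death, and a drug started before injection.

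- Stop date July 2022, day missing: imputed to 31 July, which is after 17 July, so no cell.
- Stop date 2022, day and month missing: imputed to 31 December, so no cell.
- No stop date: not imputed, flagged as continuing, so P, C.

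The record with least information is kept and the two with more are lost.

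**Effect of the lock.** SAP Section 6.8 plans a primary analysis after Day 29 and a final analysis after Day 361. A drug with no stop date at the first lock is C or P, C. If a stop date of Day 46 is entered later, the same drug has no cell.

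**Row and column limits.** The second start row runs to 28 days after injection, read here as injection + 28 (Day 29), while the end column stops at injection + 27 (Day 28). A product given only on Day 29 passes the row and fails the column. A drug started on Day 29 with no end date is classed C, although Day 29 lies outside the SAP Section 6.1 period.

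**The case against.** A reader might infer that immunosuppressant and steroid courses spanning the Day 29 response are undercounted, so that balance between arms in treatments affecting HAI titers cannot be judged. The documents do not support this. The line for those products in SAP Section 6.2.4 rests on administration at any time up to 28 days and has no end-date condition; a course running to Day 45 meets it. It would be affected only if programmers first filtered on the Table 8 class, which the SAP does not say. Exclusion from the per-protocol sets goes through significant protocol deviations (SAP Section 6.2.5, Protocol Section 6.5.2), not through Table 8. Exclusion Criteria 9 and 15 also limit planned use of such drugs.

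Nor are all long courses lost: those with a completely missing end date are kept by the footnote.

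It can also be said that Table 8 is silent on late end dates and does not order their removal. That is fair as to intent. But the table is the stated classification rule, and a literal program would assign such drugs to neither class.

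Finally, a right-hand column may have been lost when the table was read from PDF. The third start row gives this some force, since no known end date could fall in either visible column. Against it, the header and every row show two end-date entries, the legend has only two classes, and the missing-end-date footnote is attached to the injection + 27 column. A lost column is unlikely, though it cannot be excluded from the text.

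The one-day product on Day 29 is only a label mismatch, because it falls outside the 28-day period in any case.

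**Conclusion.** The gap is real and minor. As written, Table 8 leaves unclassified any medication that overlaps Days 1–28 and has a known end date after Day 28, or a partial one imputed past it. The outputs exposed are the any-concomitant-medication count and the preferred-term table. Both can be too low, and both can change between locks for reasons unrelated to exposure.

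The size cannot be given: the documents contain no medication-use rates. The summaries count participants, so someone with another classified medication still enters the overall count and is lost only from the affected preferred term.

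The conclusion assumes that the table was read completely, that it is programmed literally, and, for lock dependence, that an ongoing drug carries no end date until one is entered and that the summaries are repeated at the later analysis. No effect on the immune-modifying treatment line, per-protocol membership or the co-primary analyses is shown.

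**What to change.** In Table 8, change the second end-date column to any end date on or after the injection date, including ongoing or completely missing. Keep P, C for a start before injection and C for a start within the 28-day period. Set the limit of the second start row to injection + 27 days, to match SAP Section 6.1, and begin the third row after that. A drug is then concomitant when its interval overlaps the period, so every no-cell case in the table above becomes P, C or C, and a later stop date no longer changes the class.

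The cost is one column heading, the row limits and the matching programming condition. No new data are needed; any summaries already produced under the literal rule would have to be rerun.
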